
 
• To evaluate the safety of mRNA-1273 booster or third dose
 
	
 
• Solicited local and systemic ARs through 7 days after booster or third dose
 
• Unsolicited AEs through 28 days after booster or third dose injection
 
• MAAEs through the entire study period
 
• SAEs through the entire study period
 
• AESIs through the entire study period
 
• AEs leading to discontinuation from study participation post-booster or post-third dose through the last day of study participation
 

 
• To evaluate safety of mRNA-1273.214 booster dose
 
	
 
• MAAEs through the entire study period
 
• SAEs through the entire study period
 
• AESIs through the entire study period
 
• AEs leading to discontinuation from study participation post-booster dose or post-third dose through the last day of study participation
 

 
• To infer effectiveness of the mRNA-1273 booster or third dose by establishing noninferiority of Ab response after the booster dose or third dose in children in Study P204 compared with postprimary series in adult recipients of mRNA-1273 in the clinical endpoint efficacy trial (Study P301)
 
	
 
• GM value of post-booster (post-third dose) Ab in Study P204 compared with post-primary series (post-Dose 2) in adults (18 to 25 years) in Study P301
 
• Seroresponse rate of post-booster (post-third dose) from baseline (pre-Dose 1) compared with postprimary series (post-Dose 2) from baseline (pre-Dose 1) in the adults (18 to 25 years) in Study P301, using 4-fold rise definition 
 
• Seroresponse is defined as a titer change from baseline (pre Dose 1) below the LLOQ to <math>\geq 4 \times</math> LLOQ, or at least a 4 fold rise if baseline is <math>\geq</math> LLOQ
 
 
 
• For Part 3, the GM value and SRR of post-third dose Ab in Study P204 compared with
 

Objectives	Endpoints
	postprimary series (post-Dose 2) from adults ( $\geq$ 18 years of age) in Study P301
Secondary Objectives	Secondary Endpoints

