### **Part 3 Hypothesis Testing for Third Dose**

#### Third dose coprimary endpoint 1: antibody GM at BD-Day 29

The null hypothesis  $H^1_0$ : immunogenicity response to mRNA-1273 third dose as measured by Ab GM at BD-Day 29 in children in Study P204 is inferior compared with Ab GM that at Day 57 (28 days after Dose 2) in the primary series of mRNA-1273 in adults ( $\geq 18$  years of age) in Study P301.

The noninferiority in Ab GM at BD-Day 29 in children receiving mRNA-1273 as a third dose in Study P204 compared with Ab GM at Day 57 in the primary series in adults ( $\geq 18$  years of age) in Study P301 will be demonstrated by the GMR (1-alpha) CI lower bound  $\geq 0.67$  using a noninferiority margin of 1.5, where the 1-alpha can be 97.5% or 95% depending on the alpha level of 0.025 or 0.05 used for the hypothesis testing. The GMR is defined as the ratio of GM value of Ab at BD-Day 29 in Study P204 compared with Ab GM value at Day 57 (28 days after Dose 2) following the primary series of mRNA-1273 in Study P301.

#### Third dose coprimary endpoint 2: antibody seroresponse rate at BD-Day 29

The null hypothesis  $H^2_0$ : immunogenicity response to mRNA-1273 third dose as measured by SRR at BD-Day 29 in children in Study P204 is inferior compared with SRR at Day 57 (28 days after Dose 2) following the primary series of mRNA-1273 in adults ( $\geq 18$  years of age) in Study P301.

The noninferiority in SRR at BD-D29 in children receiving mRNA-1273 as a third dose in Study P204 compared with SRR at Day 57 (28 days after Dose 2) following the primary series of mRNA-1273 will be demonstrated by the SRR (1-alpha) CI lower bound  $\geq -10\%$  using the noninferiority margin of 10%, where the 1-alpha can be 97.5% or 95% depending on the alpha level of 0.025 or 0.05 used for the hypothesis testing. The SRR difference is defined as the SRR at BD-Day 29 in Study P204 minus the rate at Day 57 (28 days after Dose 2) following the

primary series of mRNA-1273 in adults in Study P301. The SRR is defined as a titer change from baseline (pre-Dose 1) below the LLOQ to  $\geq 4 \times$  LLOQ, or at least a 4-fold rise if baseline is  $\geq$  LLOQ.

Part 3 third dose primary immunogenicity objective will be considered to be met if the noninferiority in the age group compared with the adults ( $\geq 18$  years of age) is demonstrated based on both coprimary endpoints.

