For Part 3 third dose primary immunogenicity analysis of GM in children receiving a third mRNA-1273 dose, an analysis of covariance model will be performed to assess the difference in the immune response at BD-Day 29 between children receiving mRNA-1273 third dose in Study P204 and adults ( $\geq 18$  years of age) receiving mRNA-1273 booster dose (third dose) in Study P301. In the analysis of covariance model, antibody titers at BD-Day 29 in P204 children and titers at Day 57 in P301 young adults will be a dependent variable, and a group variable (children in Study P204 and adults in Study P301) will be the fixed effect. The GMT will be estimated by the GLSM from the model and its corresponding 95% will be provided for each group. The GMR for children in Study P204 with respect to adults in Study P301 will be estimated by the ratio of GLSM from the model and the corresponding 95% CIs will be provided. The 95% CI for GMR will be used to assess the between-group difference in immune response at BD-Day 29 in children in Study P204 compared with Day 57 following the primary vaccine series in adults in Study P301. The noninferiority of post-third dose GM in children will be considered demonstrated if the lower bound of the (1-alpha) CI of the GMR is  $\geq 0.67$  based on the noninferiority margin of 1.5.

The number and percentage of participants with seroresponse due to vaccination will be provided with 2-sided 95% CI using the Clopper-Pearson method at each postbaseline time point with Day 57 being of the primary interest in the analyses for the mRNA-1273 primary series in Part 1

or Part 2. The SRR difference with 95% CI (using Miettinen-Nurminen score method) at Day 57 will be provided between children receiving mRNA-1273 primary series in Study P204 Part 1 or Part 2 and young adults of 18 to 25 years of age receiving mRNA-1273 primary series in Study P301. For each pediatric age group in Part 1 or Part 2, the noninferiority of SRR will be considered demonstrated if:

- The lower bound of the 95% CI of the SRR difference is  $\geq -10\%$  based on the noninferiority margin of 10%, AND
- The SRR difference point estimate  $\geq -5\%$  (minimum threshold).

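### The Part 3 third-dose geometric-mean analysis in 8.5.3 names the wrong P301 reference group in two of its sentences (booster recipients, then young adults), against the hypothesis and the power statement

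*Protocol*

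**What the plan says.** Protocol 8.2, under the Part 3 third-dose hypotheses, sets the GM comparison as "children receiving mRNA-1273 as a third dose in Study P204 compared with Ab GM at Day 57 in the primary series in adults" aged 18 or older in Study P301. The power statement in 8.3 assumes 289 children and 289 P301 adults aged 18 or older after the 100 µg primary series. The third-dose seroresponse analysis in 8.5.3 uses the same reference, and Table 2 has a Part 3 endpoint line naming adults 18 or older.

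The 8.5.3 paragraph for the third-dose GM coprimary endpoint describes the reference in three ways:

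- its opening sentence compares children at BD-Day 29 with adults 18 or older "receiving mRNA-1273 booster dose (third dose) in Study P301";
- its model sentence says "antibody titers at BD-Day 29 in P204 children and titers at Day 57 in P301 young adults will be a dependent variable";
- its interpretation sentence says "compared with Day 57 following the primary vaccine series in adults in Study P301".

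The synopsis version of this paragraph opens with the correct reference (adults 18 or older, Day 57, primary series), but its model sentence still has "titers at Day 57 in P301 young adults will be a dependent variable".

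On the interval, 8.5.3 says "The 95% CI for GMR will be used to assess the between-group difference in immune response at BD-Day 29 in children", and then bases the success rule on the (1-alpha) interval.

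**The concern.** The reference group is the denominator of the geometric mean ratio (GMR) and so part of the definition of a coprimary endpoint. Booster recipients and young adults are different reference groups from the one that was hypothesised and powered, and each would give a different GMR.

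Young adults is not loose wording here. Section 8.2 describes the 18 to 25 group as a separate random subset (305 participants, 296 with Day 57 results), distinct from the 1055 adults aged 18 or older. It allows the 18 to 25 group only as a possible sensitivity comparator when adults 18 or older are primary. A programmer who followed the model sentence literally would load another data set.

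Part 3 is open label, and both Day 57 reference GMTs are already printed in the protocol. A choice between the sentences made at the time of analysis would therefore be made with comparator results in view.

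**Working it through.** **Inputs.** From 8.3: 289 per group, SD 1.5 on the natural-log scale, true GMR 1.0, margin 1.5, two-sided alpha 0.025. From 8.2: success bound 0.67; Day 57 GMT 1081.1 (95% CI 1019.8 to 1146.1, n = 1055) for adults 18 or older, and 1301.3 (1172.3 to 1444.5, n = 296) for ages 18 to 25.

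**Plan's own figure.** Standard error of the log ratio = 1.5 × √(2/289) = 0.1248. With margin ln 1.5 = 0.4055, power = Φ(0.4055/0.1248 − 2.241) = 84.3%, so the stated 84% reproduces. With the rounded bound, −ln 0.67 = 0.4005 and power is 83.4%. At alpha 0.05 the two figures are 90.1% and 89.4%.

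**Shift between references.** 1301.3/1081.1 = 1.204. If children equal adults 18 or older, the true GMR against the 18 to 25 group is 1/1.204 = 0.831.

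**Effect on power.** Power = Φ((ln GMR − ln 0.67)/se − z), with z = 2.241 at alpha 0.025 or 1.960 at alpha 0.05. For the 18 to 25 reference, ln 0.831 − ln 0.67 = −0.1854 + 0.4005 = 0.2151, and 0.2151/0.1248 − 2.241 = −0.52, which gives 30%.

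| SD | Reference at Day 57 | True GMR | Power, alpha 0.025 | Power, alpha 0.05 |
|---|---|---|---|---|
| 1.5 | 18 or older | 1.00 | 83% | 89% |
| 1.5 | 18 to 25 | 0.83 | 30% | 41% |
| 0.95 | 18 or older | 1.00 | 99.8% | 99.9% |
| 0.95 | 18 to 25 | 0.83 | 68% | 78% |

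The SD of 0.95 is an assumption. The reported confidence intervals imply 0.91 (18 to 25) and 0.97 (18 or older).

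**Booster reference.** The protocol gives no P301 post-booster titer. If it were 1.5 times the 18-or-older Day 57 GMT (assumption), power would be about 1% to 2%; at 2 to 3 times it would be essentially nil.

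**Interval level.** Under the multiplicity rules in 8.5.3, the third dose is tested at 0.05 if the Part 3 primary series succeeds at 0.025, and at 0.025 if it does not. A 95% interval is therefore the right level in the success branch and the wrong one only in the failure branch. At SD 1.5 the lowest passing GMR is 0.67 × exp(2.241 × 0.1248) = 0.886 with a 97.5% interval and 0.67 × exp(1.960 × 0.1248) = 0.856 with a 95% interval.

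**The case against.** The strongest reply is that the intended reference is not in doubt. The hypothesis, the power statement, the Part 3 line of Table 2, the seroresponse coprimary and the opening sentence of the synopsis paragraph all point to adults 18 or older at Day 57. Even in 8.5.3 no P301 post-booster titers enter the model, so the booster comparison could not be run as described. The young-adult phrase matches the Part 1 and Part 2 booster paragraph and looks carried over. This stands as evidence of intent. It does not make the two sentences harmless, because the sentence that specifies the model is the one with the wrong group, and that group has its own data set.

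A reader might infer several stronger things that the documents do not support:

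- **A 95% interval set against a 97.5% decision rule, doubling alpha.** The success rule already uses the (1-alpha) interval, which 8.2 defines as 97.5% or 95%. The 0.025 assigned at the outset belongs to the Part 3 primary series. One-sided error would rise from 0.0125 to 0.025 only if someone ignored the success sentence in the failure branch.
- **Pass marks of 872 against 724** (0.67 times each GMT). Success depends on the lower confidence bound. At SD 1.5 and alpha 0.025 the child GMT needed is about 958 against adults 18 or older (0.886 × 1081.1) and 1153 against ages 18 to 25 (0.886 × 1301.3). The 1.20 ratio is what carries over.
- **A rival estimand in Table 2.** The line "GM value of post-booster (post-third dose) Ab in Study P204 compared with post-primary series (post-Dose 2) in adults (18 to 25 years") carries a third-dose parenthesis, but Table 2 also has its own Part 3 line, and 8.5.3 elsewhere calls the Part 1 and Part 2 booster a third dose.
- **A conflict across the whole third-dose analysis.** It is confined to the GM coprimary; the seroresponse analysis is consistent.

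**Conclusion.** Wrong as written. Of the three descriptions in the 8.5.3 third-dose GM paragraph, only adults at Day 57 after the primary series agrees with the hypothesis, the power statement, the Part 3 endpoint line and the seroresponse coprimary. The error could decide the result: at alpha 0.025, using the 18 to 25 group would cut power from about 83% to 30% at the planning SD of 1.5, or from 99.8% to 68% at an SD near 0.95. These figures assume that children truly equal adults 18 or older, that the observed P301 GMTs stand in for the true ones, and 289 per group.

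The fixed 95% interval is a lesser reporting inconsistency that matters only if the Part 3 primary series fails. The design, the sample size and the stated 84% power are sound.

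**What to change.** - In the 8.5.3 third-dose GM paragraph, replace the P301 booster reference with P301 adults aged 18 or older at Day 57 after the mRNA-1273 primary series, as the synopsis opening sentence already has it.
- In the model sentence of that paragraph and of its synopsis counterpart, change young adults to adults aged 18 or older.
- Tidy-up: in both paragraphs, give the third-dose GMR interval at the (1-alpha) level in place of the fixed 95%.
- Optional: delete the third-dose parenthesis from the 18 to 25 endpoint lines in Table 2 and the synopsis table.

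The cost is a text correction in a protocol amendment before the third-dose analysis. The number of participants does not change, and with the reference fixed, power is 84.3% at alpha 0.025 and 90.1% at alpha 0.05 (margin ln 1.5).

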### **Multiplicity Adjustment Between Age Groups:**

A hierarchical sequential hypothesis testing (fixed-sequence method) will be used to adjust multiplicity to preserve the family-wise Type I error rate (alpha = 0.05), starting with the oldest age group, followed by the middle age group, and then followed by the youngest age group. The primary series immunogenicity coprimary endpoint hypotheses for the oldest age group (6 years to < 12 years of age) will be tested first at alpha level of 0.05 in Part 1 expansion or Part 2. If the testing in the oldest age group is statistically significant (meeting the noninferiority success criteria of the coprimary endpoints), the alpha level of 0.05 will be passed to the testing of the primary series coprimary endpoint hypotheses in the middle age group (2 years to < 6 years of age) in Part 2. If the testing in the middle age group is statistically significant at alpha level of 0.05, then the alpha 0.05 is preserved for testing the primary series coprimary endpoint hypotheses in the youngest age group (6 months to < 2 years of age) in Part 2.

If the hypothesis testing is statistically significant for all the primary series primary immunogenicity endpoints in Part 2, the alpha 0.05 is preserved for the hypothesis testing for the booster dose primary immunogenicity endpoint in Part 1 or Part 2, starting in the oldest age group (6 years to < 12 years of age), then the middle age group (2 years to < 6 years of age), followed by the youngest age group (6 months to < 2 years of age) for booster dose in applicable age groups in Part 1 or Part 2. The testing will continue through the sequence only until an endpoint is not statistically significant (did not meet specified noninferiority success criteria of any primary endpoint) in Part 1 or Part 2, in which case the testing will stop. If the hypothesis testing for all the booster dose primary endpoints in Part 2 is statistically significant (meeting the noninferiority success criteria of the primary endpoints), the alpha level of 0.05 will be passed to the hypothesis testing in Part 3.

In Part 3, half of the type I error rate 0.05 by alpha-splitting will be initially allocated to the hypothesis testing for the primary series immunogenicity coprimary endpoints, which will be tested initially at alpha level of 0.025. The second 0.025 will be reserved for Part 3 third dose hypothesis testing, and a fallback method will be used if applicable.

- If the testing of the primary series coprimary endpoints in Part 3 is statistically significant at alpha level of 0.025 (meeting the noninferiority success criteria of the coprimary endpoints), a total of alpha 0.05 will be preserved for the hypothesis testing of the Part 3 third dose immunogenicity coprimary endpoints.
- If the hypothesis testing of the primary series coprimary endpoints in Part 3 is not statistically significant at alpha level of 0.025 (not meeting any of the specific noninferiority success criteria of the coprimary endpoints), the remaining alpha level of 0.025 reserved will be used for the hypothesis testing of the Part 3 third dose immunogenicity coprimary endpoints. Further, if the hypothesis testing of the third dose coprimary endpoints in Part 3 is statistically significant at alpha level of 0.025, the unused alpha 0.025 will be passed back to re-testing of primary series coprimary endpoint hypothesis in Part 3 at alpha level of  $0.025+0.025=0.05$  (a fallback method).

#### **8.5.4 Efficacy Analysis**

To evaluate the incidence of COVID-19 after vaccination with mRNA-1273 or placebo, the incidence rate will be provided by vaccination group, dose level, and age group, calculated as the number of cases divided by the total person-time. Participants in Part 1 and Part 2 of the study and in different age groups who receive the same mRNA-1273 dose level (if applicable) may be combined in the analysis.

For serologically confirmed SARS-CoV-2 infection or COVID-19, regardless of symptomatology or severity, infection rate will be provided by vaccination group, dose level, and age group. The same analysis will be conducted for asymptomatic SARS-CoV-2 infection.

The secondary efficacy analyses will be performed on the PP Set, with sensitivity analyses in FAS, modified Intent-to-Treat (mITT) Set, and modified Intent-to-Treat-1 (mITT1) Set. Analyses of the efficacy endpoints in Part 2 will be performed for the randomized blinded phase. Additional exploratory analyses will be conducted in the blinded and unblinded phases for participants randomized to mRNA-1273 in Part 2, and in the unblinded phase for participants who are originally randomized to the placebo arm and cross-over to mRNA-1273 after use of any COVID-19 vaccine is authorized or licensed for the participant's age group.

